Regulatory Authorities (e.g. Food and Drug Administration	Audit clinical trial for Subject protection and data integrity
Investigator/Site Staff	Collection and assessment of data for accuracy and completeness

Alternatives to Participation

Subjects are not required to participate in this research study. As an alternative to study participation, subjects will receive wound care treatment per physician discretion.

1. Trial Objectives

The objective of this trial is to evaluate percent change from baseline in tissue oxygenation (via oxygen saturation, S_tO_2) in Celliant and Control treated groups 12 weeks post initial application, as measured by hyperspectral imaging in 254 evaluable patients total when a Celliant® Diabetic Medical Sock (n=127) is worn over the patients dressing as compared to wearing a Control Medical Sock (n=127). Enrollment may include up to 2500 total subjects to meet the Key Secondary Endpoint. The Key Secondary Endpoint is to compare the incidence of complete wound closure of Celliant and Control treated groups 12 weeks post initial application*. Other secondary outcomes include wound evaluation at 3 months post complete wound closure, accelerated wound closure as measured by changes in area, depth and volume as well as treatment compliance and assessment of pain reduction.

*if the study wound is deemed closed on the week 12 visit, the patient will continue using the sock and the wound will be evaluated on week 14 to confirm healed state.

2. Selection and Withdrawal of Subjects

Inclusion Criteria:

- Diagnosis of diabetes mellitus
- Subject is willing and able to wear a sports-style tube sock at least 22 hours a day.
- Ankle Brachial Index (ABI) ≥0.5 (bedside ABI is acceptable for screening purposes as the formal imaging ABI may not be resulted prior to surgery) or toe pressure of ≥30mmHg
- One or more diabetic foot ulcers (only one will be treated) that are located in the ankle area or below that has persisted a minimum of 30 days prior to the Screening visit
- Diabetic Foot Ulcers ≥0.5cm² and ≤16cm²
- Ulcer grade I or II, Stage A, I or II Stage B, according to University of Texas Wound Classification System
- 22 years of age or older

Exclusion Criteria:

- Subject has untreated osteomyelitis
- Ulcers within 5cm of target ulcer or connected by fistulas
- Ulcer has decreased by 30% or more at the end of the run-in period
- Subject has active untreated cellulitis
- Subject has active untreated charcot

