- Major immunodeficiency including HIV.
- Is pregnant or plans to become pregnant
- Is nursing or actively lactating

Celliant Clinical Trial Protocol
PI: [name]
Protocol #: HGX2020-01

 Developmental disability/significant psychological disorder that in the opinion of the investigator could impair the subject's ability to provide informed consent, participate in the study protocol or record study measures, including untreated schizophrenia, bipolar disorder and psychiatric hospitalization within the last 2 years.

 Active alcohol or substance abuse in the opinion of the investigator that could impair the subject's ability to provide informed consent, participate in the study protocol or record study materials

Withdrawal of Subjects

Subjects may withdraw from the study at any time at their own request, or they may be withdrawn at any time at the discretion of the PI for safety, behavioral, or administrative reasons. If a subject does not return for a scheduled visit, every effort should be made to contact the subject, per institutional protocol. In any circumstance, every effort should be made to document subject outcome. The Investigator should inquire about the reason for withdrawal, request that the subject return for a final visit, if applicable, and follow up with the subject regarding any unresolved AE's.

Any related SAE occurring within 14 days following subject discontinuation must be reported to Hologenix and be followed up until stabilization or resolution. If the Subject withdraws from the study, and also withdraws consent for disclosure of future information, no further study evaluations will be performed, and no additional data will be collected. The PI may retain and continue to use any data collected before such withdrawal of consent.

The Investigator may choose to withdraw their own participation or discontinue a Subject from study with or without their consent for any of the following:

- Adverse Events
- Non-compliance
- Safety
- Complications
- Unforeseen events

A patient who experiences the noted changes, relative to previous measures, in the following parameters will be terminated early from study participation

- An increase in ulcer size by 50% or more prior to debridement from previous visit.
- An increase in pain rating by 50% or more from previous visit.
- Presence of infection as determined by 2 more bacterial infection indicators that requires treatment outside the study scope

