- Presence of osteomyelitis that requires treatment outside the study scope.
- Need for wound management outside the study scope

Celliant Clinical Trial Protocol
PI: [name]
Protocol #: HGX2020-01

 Or for any reason that may, in the opinion of the Investigator, affect negatively the wellbeing of the subject.

If for any reason the subject is withdrawn from the clinical investigation, the Investigator will inform the subject accordingly.

3. Clinical Investigation Plan

Description of Trial Design

This study is designed as a prospective, multi-center, double-blind, 1:1 randomized clinical trial to assess the clinical safety and efficacy of Celliant® Diabetic Medical Socks to increase tissue oxygenation and complete wound closure.

Investigational Sites

University of Texas Southwestern, Department of Plastic Surgery

PI: [name], DPM, MPH

Location: Dallas, TX

Parkland Hospital, Department of Plastic Surgery

PI: [name], DPM Location: Dallas, TX

Duration of Subject Participation

- Screening: Within 7 days Run-In initiation
- Run in Evaluation: 2 weeks of evaluation
- Treatment period: Up to 12 weeks
- Follow-up period: Up to 3 months post wound closure event
- Total duration of subject participation: Up to 28 weeks

Screening and Enrollment

Patients who present to the investigator's institution (through clinic admission, direct transfer from another facility, or through the emergency room) may be recruited to participate in the study. No direct marketing for subject recruitment will be done.

Patients approached for study participation will be at least 22 years of age at the time of consent, will undergo wound assessment, and meet all eligibility requirements. Those meeting eligibility criteria for the study will have the study explained to them by the Investigator. An Informed Consent Form will be provided to sign according to Section 11 prior to undergoing any study procedures. Patients will be encouraged to ask questions of the investigators. It will be made clear to the patient that not participating in the study will in no way influence the treatment plan or the relationship with the physician.

Celliant Clinical Trial Protocol
Protocol #: HGX2020-01

Wound Selection

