- 8. Perform SPP and tcPO2 measurements at Visit 4 (maybe be taken instead at visit 5 or 6 if subject has not been wearing their treatment sock leading up to the visit or misses this visit).
- 9. Collect all relevant concomitant medication
- 10. Perform pain assessment.
- 11. Redress the wound with standard of care (if wound is still active) and apply Celliant Active or Control Sock and apply offloading (if indicated).
- 12. Wound will be offloaded.
- 13. Provide subject with any additional medical socks needed until the next visit. Instruct the subject to change the socks if they become wet, soiled, or bloody and under any conditions dictated by PI instructions. Instruct the subject that they must wear the sock at all times and that including the 3 hours leading up to the next study visit.

Study Visit - Wound Closed

- 1. The study wound is defined as closed when there is complete skin re-epithelialization without drainage or dressing requirements confirmed by the evaluating physician at 2 consecutive study visits 2 weeks apart.
- 2. At this visit the subject will perform the EOS evaluation and enter the follow-up phase of the study.

Study Visit 12/EOS

- 1. If the study wound closes prior to the 12-week study mark, subjects will perform EOS visit at the time of wound closure. See Study Visit Wound Closed.
- 2. A subject whose wound does not close completely by week 12 will exited from the study after the week 12 wound evaluation.
- 3. Document study compliance information from the subject
 - a. Amount of time the sock was worn throughout the week
 - b. Was it worn during the day/night?
 - c. When/why the sock was changed.

- d. Has the sock been on in the 3 hours leading up to the appointment?
- 4. Remove sock and dressing and immediately perform hyperspectral imaging of the dorsal and plantar aspects of the foot if wound is active or closed.
- 5. Assess target ulcer (if wound has closed, document as such, perform steps 7-12 and skip to Study Visit Wound Closed).
- 6. If the subject still has a large enough wound, collect 4 tissue samples. Two in RNA later and two in DNA/RNA shield.
- 7. Perform standardized photography of the study wound.
- 8. Assess the ulcer area (cm²), perimeter (cm), and greatest depth (cm) using the inSight device.
- 9. Perform SPP if wound is active or closed.
- 10. Perform tcpO2 if wound is active or closed.
- 11. Perform pain assessment
- 12. Ask the subject if they thought they were in the active or control group

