- 13. Administer DFS-SF
- 14. Collect all relevant concomitant medication
- 15. Redress the wound per physician-directed standard of care.

Study Visit Follow up

- 1. If the subject's wound closes within the 12-week treatment window, they will enter the follow up phase of the study.
- 2. At 3 months post closure, wound evaluation will be performed as outlined below. This follow-up visit will be in person. In the event that an in-person visit is not possible, a telehealth visit may be performed and documented as such.
 - a. Assess the study wound to determine that it remained closed
 - b. If the study wound has reoccurred
 - i. record the date of reoccurrence
 - ii. measure the size of dehiscence or re-ulceration
 - iii. exit the subject from the follow up phase
 - c. Assess the study foot for new sites of ulceration
 - i. record the date of reoccurrence
 - ii. measure the size of dehiscence or re-ulceration
 - iii. exit the subject from the follow up phase

Detailed Study Operations

Medical Status/History

• The New York Heart Association (NYHA) Functional Classification System: This system will be used to classify stage of heart failure. The New York Heart Association (NYHA) functional classification system is used to classify the stage of heart failure from Class I to IV (as shown in the table below). This system relates symptoms to everyday activities and the patient's quality of life.

Class	Patient Symptoms
Class I (Mild)	No limitation of physical activity. Ordinary physical activity does not cause undue fatigue, palpitation, or dyspnea (shortness of breath).
Class II (Mild)	Slight limitation of physical activity. Comfortable at rest, but ordinary physical activity results in fatigue, palpitation, or dyspnea.
Class III (Moderate)	Marked limitation of physical activity. Comfortable at rest, but less than ordinary activity causes fatigue, palpitation, or dyspnea.
Class IV (Severe	Unable to carry out any physical activity without discomfort. Symptoms of cardiac insufficiency at rest. If any physical activity is undertaken, discomfort is increased.

- Body Mass Index (BMI): BMI is calculated as the ratio of body weight in kilograms (kg) to height in meters squared (m²).
- Medical History: The following information will be collected from each subject
 - previous ulcer history
 - amputation history
 - lower extremity bypass
 - lower extremity angioplasty
 - coronary artery bypass surgery
 - cardiac angioplasty
 - arthritis
 - liver disease

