The primary population for the effectiveness analyses will be the intent-to-treat (ITT) population, which will include all randomized subjects regardless of whether the socks were ever worn. Subjects will be assessed to the group to which they were randomized, regardless of whether they were provided the wrong socks.

A secondary population for effectiveness analyses will be the (AT) population, including subjects that attempted to put on the sock for any amount of time. These subjects will be analyzed according to the type of socks (Celliant or Placebo) they received. This population is also the safety population, which is the population used for all safety analyses.

A third population is the modified full analysis set (mFAS), which consists of all subjects that report wearing the sock as directed for at least 10 days.

Sample Size Justification

Assuming a 2-sided alpha at 0.05, and a power of 0.85, the true mean difference at 12 weeks between groups in percent change in tissue oxygenation as measured by hyperspectral imaging is estimated to be 8.2 with a standard deviation of 21.7. At a 1:1 allocation of experimental to control subjects, a total of 254 evaluable subjects are required. The sample size will increase to account for attrition at Week 12.

Analyzing the sample size for the key secondary endpoint of incidence of complete wound closure suggests a much large trial is need. Specifically, at 2500 evaluable total subjects, there would be approximately a power of 0.85 to detect a difference in incidence of complete wound closure at 12 weeks if the expected incidence of complete wound closure was 25% in the experimental group, and 20% in the control group, an absolute difference of 5% between the experimental group and the control group.

Primary Efficacy Analyses

The primary efficacy endpoint is an inferential test of whether the Treatment Group (Celliant[®] Diabetic Medical Sock) percent change in tissue oxygenation (via oxygen saturation, S_tO₂) compared to the Control Group (placebo sock) at 12 weeks is superior.

Effectiveness variables will be analyzed relative to the mean of the Weekly visit 0 and -1 tissue oxygenation measurements. For purposes of statistical analysis, this mean will be referred to as the baseline.

The hypotheses are:

```
H0: %ChgPerfCelliant ≤ %ChgPerfPlacebo
Ha: %ChgPerfCelliant > %ChgPerfPlacebo
```

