A mixed model repeated measures (MMRM) will be utilized to model percent changes in tissue oxygenation by visit through 12 weeks from baseline to provide the contrast statement at 12 weeks between groups. Included in the model will be treatment group, the stratification variables of wound size (as a continuous variable) and study site. Success on this endpoint requires that the 12-week treatment group contrast difference is α <0.025. There is no interim analysis for the primary endpoint. The primary endpoint is based on a fixed study design. Regulatory activities for all but the key secondary endpoint will begin if this primary endpoint is met.

Interim Analysis for the Key Secondary Endpoint

The key secondary endpoint will only be tested for significance if the success criterion for the primary endpoint are met at the time of the primary endpoint analysis in 254 evaluable subjects, which is the interim analysis for the key secondary endpoint.

The key secondary endpoint is an inferential test of whether the Treatment Group (Celliant sock) incidence of complete wound closure rate (CWCR) compared to the Control Group (placebo sock) at 12 weeks is superior.

The hypotheses for this endpoint are:

```
H0: CWCR Celliant ≤ CWCR Placebo
Ha: CWCR Celliant > CWCR Placebo
```

The key secondary endpoint of incidence of complete wound closure at 12 weeks will be blinded except to the unblinded Interim Analysis Committee (IAC) until the final analysis for this endpoint is conducted. Since the estimated sample size for the key secondary endpoint is anticipated to be many times larger than for the primary endpoint and there is some uncertainty relative to the anticipated treatment effect, the hierarchical design allowing for the testing of the key secondary endpoint, and then the use of the adaptive group sequential design to allow for the potential of sample size re-estimation is required for efficiency.

The IAC is comprised of an unblinded statistician and a subject area medical expert whose sole responsibility is to analyze the key secondary endpoint at 254 evaluable subjects to determine, according to the Lan-Demets O-Brien Fleming alpha spending function, tested at half of the trial information:

- 1) The criterion of early stopping for efficacy for CWCR is met at half of the trial information,

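### No rule counts subjects terminated with an open wound as not closed, so the missing-data section can impute closure for them or drop them; the week assigned to an early EOS image is also unstated

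*Combined protocol and SAP*

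**What the plan says.** All references are to the combined protocol and SAP.

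**Closure (key secondary endpoint)**
- *Withdrawal of Subjects* (Section 2) lists changes that end participation early. They include "An increase in ulcer size by 50% or more prior to debridement from previous visit", a 50% rise in pain rating, infection or osteomyelitis needing treatment beyond the study, and "Need for wound management outside the study scope".
- *Study Visit - Wound Closed* (Section 3) requires closure to be "confirmed by the evaluating physician at 2 consecutive study visits 2 weeks apart".
- *Analysis Population* (Section 4) sets the primary population as intent-to-treat, "which will include all randomized subjects regardless of whether the socks were ever worn".
- *Handling of Missing Data* (Section 4) sets a trigger: week-12 oxygenation or closure data missing in more than 7.5% of subjects. Past it, five imputed datasets are made for both the primary and the key secondary endpoint. An analysis without imputation is also provided. No imputation model is named, and terminated subjects are not mentioned.

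**StO2 (primary endpoint)**
- *Study Visit 12/EOS*, step 1: "If the study wound closes prior to the 12-week study mark, subjects will perform EOS visit at the time of wound closure".
- *Study Visit Follow up*: "At 3 months post closure, wound evaluation will be performed as outlined below". The *Schedule of Events Table* has no hyperspectral imaging in that column.
- *Primary Efficacy Analyses*: the mixed model is to "model percent changes in tissue oxygenation by visit through 12 weeks from baseline to provide the contrast statement at 12 weeks between groups".
- The footnote to *Trial Objectives* covers only wounds first closed at week 12: "if the study wound is deemed closed on the week 12 visit, the patient will continue using the sock", with confirmation at week 14.

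**The concern.** A subject removed because the ulcer grew by half, or because the wound needed care the study does not allow, has a known outcome. Closure was not achieved under the study's own definition. The plan does not record it as such. That subject has no week-12 assessment, so on the words of the missing-data section the closure value is missing, and imputation may return closed. If the trigger is not passed, the subject has no value in the analysis at all, although the population is all randomised subjects.

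The closure estimate also drives the interim decisions: stopping for efficacy, continuing to 508, stopping for futility, or increasing the sample size up to 2500. A coding rule left open until then would be settled with decisions depending on it.

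The secondary gap is that a subject with confirmed closure before week 12 has a last StO2 image at the early EOS visit. Whether that image enters the model at its actual visit or as week 12 is not stated.

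**Working it through.** **1. The plan's own figures.** With a difference of 8.2, SD 21.7 and two-sided 0.05 (*Sample Size Justification*), a two-sample t test needs 127 per arm, 254 in total, with power 0.851. For closure of 25% v 20% at 1250 per arm, power is 0.85. Both stated sizes reproduce. The point is about coding, not sample size.

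**2. Closure when terminated subjects are imputed or left out.** Let c be the closure rate with all randomised subjects in the denominator and open exits counted as not closed. Let d be the share terminated open. If imputation uses arm only, or these subjects are omitted, the reported rate is c/(1 − d). The documents give 25% and 20% for c. They give no d, so the range below is assumed. The plan's 5 to 15% attrition covers losses of all kinds.

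| d in each arm | Celliant | Control | Difference |
|---|---|---|---|
| counted as not closed | 25.0% | 20.0% | 5.0 points |
| 5% | 26.3% | 21.1% | 5.3 |
| 10% | 27.8% | 22.2% | 5.6 |
| 15% | 29.4% | 23.5% | 5.9 |

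**3. Subjects involved.** At d = 10% and 127 per arm, 25.4 subjects are terminated open. About 12.7 × (0.278 + 0.222) = 6.4 of them are imputed as closed. At 1250 per arm it is 125 × 0.5 = 62.5 of 250.

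**4. No true effect (20% in both arms).**
- Equal exits: difference 0.
- 10% v 5%: 0.20/0.90 − 0.20/0.95 = 1.2 points; reversed, −1.2. The pooled share is exactly 7.5%, so closure data alone would not pass the trigger, but omission gives the same shift.
- 15% v 5%: 0.20/0.85 − 0.20/0.95 = 2.5 points, half of the planned 5.

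**5. How the two gaps connect.** The trigger is met by either endpoint. Let s be the share of closers who exit before week 12 (not in the documents). If the early EOS image does not count as week 12, StO2 missing through healing is 0.225 × s, where 0.225 is the mean of 25% and 20%. That gives 5.6%, 11.3% or 16.9% for s = 25%, 50% or 75%. It passes 7.5% when s exceeds 0.075/0.225 = one third. With 5% other attrition, s above 0.025/0.225 = 11% is enough. The unstated week assignment can therefore decide whether closure is imputed.

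**6. Size of the StO2 effect.** Using week-12 completers only, the bias is 21.7 × r × [m(0.25s) − m(0.20s)]. Here m(c) = −φ(z)/(1 − c), z is the upper-c normal quantile, and r is the assumed correlation of StO2 change with healing. For r of 0.3 to 0.5 and s of 25% to 75%, it runs from −0.15 to −0.62 points against 8.2, towards no effect. The planned model also uses earlier visits. With one earlier visit, an assumed within-subject correlation of 0.7 and the same r, the bias shrinks to about 0.05 to 0.2 points.

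**The case against.** **On closure.** The endpoint is the incidence of an event that needs two confirming visits. A subject who leaves without it can be read as a non-event, just as an early healer is read as closed without a week-12 visit. The withdrawal section also asks for a final visit where applicable and for every effort to document outcome. This is a sensible reading, and it is the one recommended here. But nothing states it, and the only rule on absent 12-week closure data sends it to imputation.

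The sizes are also open to challenge, and fairly. The exit rates are assumed. An imputation model using wound size at exit would return fewer closures. With equal exits the test hardly moves: at 1250 per arm, z is 0.05/√[(0.1875 + 0.16)/1250] = 3.00 with the not-closed rule. With 10% omitted it is 0.0556/√[(0.2006 + 0.1728)/1125] = 3.05.

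**On StO2.** A reader might infer that early healers are lost to the primary analysis and that it is biased or underpowered as a result. The documents do not support that. The heading *Study Visit 12/EOS*, and a schedule that runs from visits 1-11 straight to EOS, suggest the EOS image fills the week-12 slot. Healers are imaged at every visit up to closure, and the model uses those visits. A wound first closed at week 10 is confirmed, and imaged, at week 12. Enrolment is to be raised for attrition, so a power loss calculated on 254 randomised does not describe this plan. What stands is that the assignment is unwritten, and that an EOS image used as week 12 carries a shorter exposure in healers.

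**Conclusion.** The closure point holds. Forced termination of worsening wounds, an all-randomised population, a two-visit closure definition and no coding rule together allow a known failure to be imputed as healed or dropped. The illustrative size is 25% v 20% reading as 27.8% v 22.2%, assuming 10% terminated open per arm and imputation by arm only.

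A reader might infer that the comparison is tilted towards the sock. That does not follow. Equal exits give no bias under the null, unequal exits can shift the difference either way, and the documents give no exit rates by arm. Nor is imputation certain: it depends on the 7.5% trigger, and an imputed status may come out not closed.

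The StO2 point is secondary. It is a missing sentence with a small expected effect on the primary result, towards no effect under the assumptions shown. It matters partly because it can decide whether the shared trigger is passed.

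**What to change.** 1. **Closure.** In the intent-to-treat closure analysis, including the interim, count subjects terminated with an open wound as not closed. Limit imputation to subjects whose status is truly unknown, such as those lost to follow-up. The cost is wording only. The downside is that both reported closure rates become slightly lower (25% and 20% instead of 27.8% and 22.2% in the illustration).
2. **StO2.** State in the SAP how an early EOS image is assigned. Either it enters the model at its actual visit week, or the endpoint is defined as the EOS-or-week-12 value with a note that healers then have shorter exposure. State also whether it counts as missing for the 7.5% trigger. This too is wording only.
3. **Optional.** A week-12 image with continued sock wear in healed subjects would observe the value directly. It would mean one added visit for about 14, 29 or 43 of 254 subjects (254 × 0.225 × s for s = 25%, 50% or 75%; at most 57). At 35 dollars a visit that is about 500, 1,000 or 1,500 dollars (at most about 2,000), plus imaging time and socks. It also changes exposure before the 3-month recurrence assessment, so it is a design choice and not needed to close the gap.

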Appendix 2 – Diabetic Foot Ulcer Scale – Short	
	Quality Control and Quality Assurance. Training

Celliant Clinical Trial Protocol
PI: [name]
Protocol #: HGX2020-01

Primary Study Contacts

UT Southwestern Medical Center, Department of Plastic Surgery

Principal Investigator	[name]
email	[contact]
[contact]

Parkland Hospital, Department of Plastic Surgery

Principal Investigator	[name]
email	[contact]
[contact]

Executive Summary

Title of Study Study to Evaluate Celliant Diabetic Medical Socks to Increase Tissue Oxygenation

and Incidence of Complete Wound Closure in Diabetic Foot Wounds

Protocol Number HGX2020-01

Study Purpose The purpose of this study is to demonstrate that the use of Celliant Socks

increases tissue oxygenation (via oxygen saturation, StO₂) and incidence of wound closure in subjects with diabetic foot ulcers. This study will use hyperspectral imaging and wound assessment to measure these outcomes.

Study Design This study is a prospective, multicenter, double-blind, 1:1 randomized clinical trial.

Enrollment The study will enroll 254 evaluable subjects total, 127 per arm to meet the Primary

Endpoint. Enrollment may continue up to twenty-five hundred (2500) evaluable subjects total to meet the Key Secondary Endpoint of complete wound closure.

Investigational UT Southwestern, Department of Plastic Surgery Sites Parkland Hospital, Department of Plastic Surgery

Study Duration Up to 28 weeks (including run-in and followup phase)

Efficacy EndpointsPrimary Endpoint: To compare the percent change from baseline in tissue oxygenation in Celliant and Control treated groups 12 weeks post initial application,

as measured by hyperspectral imaging.

Key Secondary Endpoint: To compare the incidence of complete wound closure of Celliant and Control treated groups 12 weeks post initial application.

Other Secondary Endpoints:

 Change in pain assessment as reported using the Visual Analog Scale (VAS)

- 2. 3-month follow-up to assess wound closure and reoccurrence
- 3. Accelerated wound closure as measured by changes in wound area, depth and volume.
- 4. Assessment of Compliance
- 5. Outcomes of Diabetic Foot Ulcer Scale Short Form
- 6. Study related AE/SAEs

Safety Endpoints The incidence of events reported

Study Groups

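### For a closed wound, EOS step 5 stops one step short of the DFS-SF and the visit routing is circular, so healed subjects could miss the only scheduled questionnaire

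*Combined protocol and SAP*

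**What the plan says.** All visit instructions cited here are in Section 3, Clinical Investigation Plan.

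- **Study Visit 12/EOS, step 5.** For the target ulcer: "if wound has closed, document as such, perform steps 7-12 and skip to Study Visit Wound Closed".
- **Study Visit 12/EOS, steps 12 to 14.** The list continues "12. Ask the subject if they thought they were in the active or control group", then "13. Administer DFS-SF", then "14. Collect all relevant concomitant medication".
- **Study Visit - Wound Closed.** Step 1 defines closure, which needs confirmation at two consecutive visits two weeks apart. Step 2 reads "At this visit the subject will perform the EOS evaluation and enter the follow-up phase of the study". There are no further steps.
- **Study Visit 12/EOS, step 1.** For early closers: "If the study wound closes prior to the 12-week study mark, subjects will perform EOS visit at the time of wound closure". It then refers the reader to the Wound Closed visit.
- **Study Visit 1-11.** Step 3 sends a closed wound to the Wound Closed visit after two named steps. Step 7 sends a closed wound to the EOS visit.
- **Study Visit Follow up.** The three-month visit has no DFS-SF.
- **Schedule of Events Table.** It is introduced as applying to each subject. It carries a single DFS-SF mark, which fits the EOS column, and does not limit it to open wounds. Concomitant medication is also marked at EOS.

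The Executive Summary lists "Outcomes of Diabetic Foot Ulcer Scale Short Form" among the other secondary endpoints. Section 4, Additional Efficacy Analyses, includes patient-reported outcomes among the comparisons between arms.

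**The concern.** A healed subject has good reason to skip step 6 (tissue from a wound that is still large enough) and step 15 (redressing the wound). Skipping a questionnaire and a medication record has no such reason, so the upper limit of 12 looks like a numbering slip. It is nonetheless the operative instruction for exactly these subjects.

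If a site acts on it, whether a DFS-SF exists depends on whether the wound closed, and closure is the key secondary outcome. The scores that remain would come mainly or wholly from non-healers, a subset formed after randomisation. The arm that heals more would lose more forms, and any quality-of-life benefit that comes through healing would be diluted.

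The plan has nothing to repair such a loss. In Section 4, Handling of Missing Data, multiple imputation covers only tissue oxygenation and wound closure. Section 4 also names a baseline DFS-SF as a baseline characteristic, but neither the baseline visit steps nor the schedule collects one. A subject who misses the EOS form would have no DFS-SF at all. Sites could also resolve the routing differently, which would make the missing data depend on site.

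**Working it through.** **Tracing the route.** No stated figure in the plan bears on this point, so the check is to follow the cross-references.

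1. Wound seen closed at week 12: EOS step 5, then steps 7-12, then the Wound Closed visit. Step 2 of that visit calls for the EOS evaluation, which is the same numbered list with the same step 5.
2. Wound seen closed at visits 1-11: step 3 leads to the Wound Closed visit and so to the EOS evaluation. Step 7 leads directly to the EOS visit, whose step 1 refers on to the Wound Closed visit.
3. On neither route does a visit instruction say expressly that a healed subject completes step 13. Equally, no instruction says that the DFS-SF is withheld.
4. The Schedule of Events places the DFS-SF at EOS without distinction. The table was read from PDF, so its column alignment is inferred, but it agrees with EOS step 13.

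Taken by itself, step 5 leaves out the DFS-SF. Taken with its destination, the text loops. Taken with the schedule, it conflicts.

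**Size of the exposure.** Inputs: 127 evaluable subjects per arm, and closure of 25% (experimental) and 20% (control), all from Section 4, Sample Size Justification and Randomization.

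- Active closers: 127 × 0.25 = 31.75
- Control closers: 127 × 0.20 = 25.4
- Total: 57.15, and 57.15 / 254 = 22.5%
- At 2500 subjects: 1250 × 0.25 + 1250 × 0.20 = 312.5 + 250 = 562.5, again 22.5%

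Let f be the share of healed subjects whose form is missed, taken as equal in both arms. The documents do not give f, so the range is shown.

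To illustrate the effect on the comparison, let healed subjects score D points better than unhealed subjects. D is not given either. Assume that the sock acts only through healing and that non-healers have the same mean score in both arms. With healing rate p, the healed share among observed forms is p(1 − f) / (1 − pf), and the arm difference is D times the difference in that share.

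| f (assumed) | Forms lost, active | Forms lost, control | Total of 254 | Observed arm difference |
|---|---|---|---|---|
| 0 | 0 | 0 | 0 (0%) | (0.25 − 0.20)D = 0.050D |
| 0.5 | 15.9 | 12.7 | 28.6 (11.25%) | (0.125/0.875 − 0.100/0.900)D = 0.032D |
| 1 | 31.75 | 25.4 | 57.15 (22.5%) | 0 |

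**The case against.** A reader might infer that the DFS-SF would be collected only from unhealed subjects. The documents do not support that. Step 5 does not end the visit. It sends the subject to the Wound Closed visit, which requires the EOS evaluation, and the EOS list contains the DFS-SF. For early closers, EOS step 1 and Visit 1-11 step 7 call for the EOS visit without shortening it. The schedule and the Patient Reported Outcomes section contain no restriction. Subjects first seen closed at week 12 are seen again at week 14 (Section 1 and the schedule footnote), which is another occasion for the form. The exclusion arises only if step 5 is applied again inside the EOS evaluation. That reading never terminates, so a site has to break the loop, and completing the whole list is at least as natural.

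This argument stands as far as it goes. It shows that the loss is possible rather than certain, and that 57 of 254 is an upper bound. The problem is clearest for wounds first seen closed at week 12, and the plan gives no distribution of closure times from which to count them.

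Two further limits also stand. The dilution to zero depends on assumptions that the documents do not support: an effect only through healing, and comparable non-healers. The DFS-SF is also outside the testing hierarchy of tissue oxygenation, closure and VAS pain, so no confirmatory conclusion depends on it.

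The objection does not remove the conflict. A healed subject's DFS-SF still depends on how each site reads a circular instruction.

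**Conclusion.** The point holds as an internal inconsistency. EOS step 5 stops just before the DFS-SF and concomitant medication, its destination points back to the same list, and the steps disagree with the schedule. A site that follows step 5 literally could miss the DFS-SF in healed subjects, making missing data on a once-only secondary endpoint depend on the outcome.

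The loss ranges from 0 to about 57 of 254 (22.5%). The upper end assumes the planned 25% and 20% closure rates and that every closer, at whatever visit, is handled by the literal step 5. The lower end applies if sites work from the schedule or complete the full EOS list. The documents do not show where in this range the trial would fall, and they do not establish that healed subjects are excluded. The correction should be made because the loss could not be recovered and is cheap to prevent.

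**What to change.** 1. In Study Visit 12/EOS, step 5, change the range from steps 7-12 to steps 7-14, so that the DFS-SF and concomitant medication are included for closed wounds.
2. Extending the range alone leaves the loop in place and could lead to the form being given twice. State in Study Visit - Wound Closed that every healed subject, including those closing before week 12, completes the DFS-SF once. Name the visit: either first observed closure or the confirming visit two weeks later.
3. Reconcile Visit 1-11 steps 3 and 7, which now give different destinations for a closed wound, with that rule.

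The cost is a short protocol clarification with the usual IRB submission. The questionnaire and the medication record are already scheduled at EOS, so no assessment is added and neither sample size nor analysis changes.
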